3.3.2 BLINDED IMAGE ASSESSMENT

Endoscopy videos and histopathology images will be scored by qualified independent central readers (CR) blinded to the visit at which the videos/images were obtained.

Endoscopic assessments will be scored both locally and centrally and histologic assessments will be scored centrally. Study central readers will receive standardized training on ^{CCI} [REDACTED]

[REDACTED] for assessment of endoscopy and histopathology (qualified gastroenterologists and pathologists, respectively). Central readers will enter scores in a study database. For histologic assessments, there will be a single central read. For endoscopic assessments, two central reader scores will be the primary scores for analyses and for confirming eligibility. In the case of adjudication for endoscopy, the third central reader (adjudicator) would score the endoscopy video independently.

Further details are available in the Image Review Charter.

4 GENERAL CONSIDERATIONS FOR DATA ANALYSES

4.1 REPORTING CONVENTIONS

The following reporting conventions apply generally to tables, listings, and graphs:

- Unless otherwise specified, the baseline value is defined as the last non-missing assessment before the first does of study treatment.
- If the date of interest occurs on or after the first dose date, the study day will be calculated as (date of interest – date of first dose) + 1.
- If the date of interest occurred prior to the first dose date, then study day will be calculated as (date of interest – date of first dose).
- Categorical data will be summarized by treatment group in terms of frequency counts and percentages.
- Continuous variables will be summarized by treatment group using descriptive statistics (the number of subjects (n), mean, median, standard deviation (SD), minimum (Min), and maximum (Max)) of the values at each visit and the change from baseline to each visit, unless specified otherwise.
- Confidence Intervals (CIs) will be presented as 2-sided 95% CIs.
- All mean, median and CI values will be formatted to one more decimal place than the measured values. SD values will be formatted to two more decimal places than the measured value. Min and Max will be formatted to the same number of decimal places as the measured value. The maximum number of decimal places reported shall be four for any summary statistic.
- All percentages will be rounded to one decimal place, unless specified otherwise. The number and percentage of responses will be presented in the form xx (xx.x), where the percentage is in the parentheses.
- Change from baseline is calculated as a post-baseline value minus the baseline value.
- All laboratory data will be reported using standard international units.
- All analysis and summary tables will include the analysis population sample size (ie, number of subjects) in the column headings.

- By-subject listings will be presented for all subjects in the relevant analysis sets, and sorted by treatment allocation, study site (if applicable), Subject ID, date, and visit. Numeric data will be listed to the same number of decimal places as recorded on the eCRF or other data source. Data collected on log forms, such as AEs, will be presented in chronological order within the subject, and age, and sex will be included in the listing, as space permits.
- SAS® Software Version 9.4 (SAS Institute Inc., Cary, NC, USA.) is to be used for all analyses including tables, listings, and figures.
- Non-pharmacokinetic and non-biomarker lab data that are continuous in nature but are less than the lower limit of quantitation (LOQ) or above the upper LOQ will be imputed as follows:
 - A value that is 1 unit less than the LOQ will be used for calculation of descriptive statistics if the datum is reported in the form of “< x” (where x is considered the LOQ). For example, if the values are reported as < 50 and < 5.0, values of 49 and 4.9, respectively, will be used for calculation of summary statistics. An exception to this rule is any value reported as < 1 or < 0.1, etc. For values reported as < 1 or < 0.1, a value of 0.9 or 0.09, respectively, will be used for calculation of summary statistics.
 - A value that is 1 unit above the LOQ will be used for calculation of descriptive statistics if the datum is reported in the form of “> x” (where x is considered the LOQ). Values with decimal points will follow the same logic as above. The LOQ will be used for calculation of descriptive statistics if the datum is reported in the form of “≤ x” or “≥ x” (where x is considered the LOQ).
- PK plasma concentration values that are below the limit of quantitation (BLQ) will be treated as 0. PD/biomarker BLQ concentration values will be treated as ½ *LOQ at all time points.
- MedDRA version 24.0 will be used to code adverse events and medical history, World Health Organization (WHO) drug dictionary version March 2020 or newest will be used for medication coding.

4.2 ANALYSIS SETS

4.2.1 SCREENING SUBJECTS ANALYSIS SET

All subjects who signed informed consent and participated in screening visit will be included in the screening subjects analysis set. The number of subjects screened will be reported, and will be used for the presentation of subject disposition. Data collected on subjects who are screened but not enrolled, i.e. study medication not received, will not be included in any analyses.

4.2.2 SAFETY ANALYSIS SET

All subjects who received at least 1 dose of study drug will be included in the safety analysis set. The Safety Analysis Set is the primary analysis set for safety analyses.

4.2.3 FULL ANALYSIS SET (FAS)

All subjects who have been treated with PRA023 with Baseline CDAI and SES-CD scores will be included in the FAS. The FAS set will be used for efficacy analysis.

4.2.4 PER-PROTOCOL(PP) ANALYSIS SET

The PP analysis set is a subset of FAS. Subjects who had significant protocol deviations will be excluded from analysis based on PP analysis set.

4.2.5 OPEN LABEL EXTENSION ANALYSIS SET

The OLE analysis set includes subjects who are randomized and received at least 1 dose of OLE drug. The analysis will be presented by the randomized treatment group.

4.3 HANDLING OF MISSING DATA

In general, missing data will not be imputed for descriptive statistics unless methods for handling missing data are specified. The handling of missing or incomplete dates for prior and concomitant medications is described in Section 5.4, and for AE onset is described in Section 7.1.

The handling of missing data in analyses of the efficacy endpoints is discussed in Section 6.2 to Section 6.4.

4.4 ANALYSIS VISIT WINDOW

The following tables present the visits assigned for efficacy and safety analyses and the corresponding ranges of treatment days (window) during which an actual visit may occur. In general, data collected at nominal visits will be used for the analysis. In case of missing assessments at a nominal visit, data collected from unscheduled visits will be slotted according to the Visit Windows of Table 2 for analysis, unless specified otherwise. If multiple unscheduled visits are slotted into the same nominal visit, the one closest to the targeted visit date will be used.

Table 2 Analysis Visit Windows

Analysis Visit ^a	Assessment	Target Day of the Visit	Analysis Visit Window (Study Day)
Induction Treatment Period			
Screening	All assessments	-35 to 0	≤ 1
Randomization (Week 0)	All assessments	1	1
Week 1	Vital Signs, CBC, hsCRP, CDAI	8	2 - 11
Week 2	Vital Signs, CBC, hsCRP, CDAI	15	12 - 28
	Fistula, Chemistry panel, Urinalysis, total sTL1A, Fecal Calprotectin	15	2 - 28
Week 6	Vital Signs, CBC, Chemistry panel, Urinalysis, Fistula,	43	29 - 57

	total sTL1A, Fecal Calprotectin, CDAI		
	IBDQ	43	2 - 57
Week 10	Vital Signs, CBC, Fistula, total sTL1A, Fecal Calprotectin, CDAI	71	58 - 78
Week 12/ET	Vital Signs, CBC, Fistula, total sTL1A, Fecal Calprotectin, CDAI	85	79 - 92
	Chemistry panel, Urinalysis, IBDQ	85	58 - 92
	Ileocolonoscopy	85	71 - 98
	ECG, Lipid panel, PDAI	85	2 - 92
Post Treatment Period			
Safety Follow-up ^b	Safety Follow-up	NA	Remain as the nominal visit

a Relative to the date of the first dose of study treatment. Day 1 = the date of the first dose of study treatment.

b No visit window will be used for the post-treatment period. The nominal CRF visit description of Safety Follow-up will be used regardless of when this visit occurs. Presented in analysis tables for safety parameters, including but not limited to electrocardiograms, clinical laboratory values, and vital signs. No visit window are needed for physical examination or pregnancy test.

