6.3 SECONDARY EFFICACY ENDPOINTS

6.3.1 DICHOTOMOUS OR BINARY ENDPOINTS

The definition of the dichotomous secondary efficacy endpoints (i.e., responders) are listed in Table 3 below.

Table 3 Definition of Secondary Binary Endpoints

Outcome	Measure	Definition	Analysis Timepoints
Clinical Remission	CDAI	Crohn's disease activity index [CDAI] < 150	Week 12
Endoscopic and clinical improvement	SES-CD and CDAI	Decrease in SES-CD ≥ 50% AND reduction in CDAI ≥ 100 points from Baseline, or CDAI < 150	Week 12
Biomarker and Clinical Composite Improvement	hsCRP and CDAI	Decrease in hsCRP or fecal calprotectin ≥ 50% from Baseline and reduction in	Week 12

		CDAI \geq 100 points from Baseline, or CDAI < 150	
Clinical Response	CDAI	Reduction in CDAI \geq 100 points from Baseline or CDAI < 150	Week 12
PRO-2 remission	Abdominal pain score and Stool frequency	Average daily abdominal pain score \leq 1 point and average daily stool frequency \leq 3 points with abdominal pain and stool frequency no worse than Baseline	Week 12
Normalization of hsCRP	hsCRP	hsCRP < ULN, among subjects whose baseline hsCRP \geq ULN	Baseline, Week 12
Normalization of fecal calprotectin	fecal calprotectin	fecal calprotectin < ULN, among subjects whose baseline fecal calprotectin \geq ULN	Week 12
Anti-drug antibody (ADA) and Neutralizing antibody (Nab)	ADA and Nab	Positive ADA at any time; Positive Nab at any time	Over time

Abbreviations: SES-CD, Simple endoscopy score for Crohn's disease; CDAI, Crohn's disease activity index; hsCRP, High sensitivity C-reactive protein; PRO-2, Two component patient-reported outcome; ADA, Anti-drug antibody; Nab, Neutralizing antibody.

The proportion of clinical remission in FAS will be analyzed according to the method similar to the sensitivity analysis for the primary efficacy endpoint, in the case of missing data in CDAI at Week 12. If the resulting lower limit of 95% confidence interval is greater than 16%, the observed remission rate for the placebo treated patients from multiple prior CD trials ([1], [7], [8], [9], [10]), the null hypothesis for the first secondary endpoint of clinical remission at Week 12 will be rejected at a 1-sided significance level of 0.025.

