6.8 MISSING DATA HANDLING

6.8.1 NON-RESPONDER IMPUTATION (NRI)

For the responder analyses as described in Table 3 of Section 6.2, unless specified otherwise, subjects who do not have sufficient measurements to determine the endpoint will be considered as non-responders (i.e., non-responder imputation (NRI)). Specifically, all subjects who discontinue from the study at any time prior to the assessment timepoint (regardless of reason) or fail to have an adequate efficacy assessment at that timepoint will be considered a non-responder.

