APPENDIX G. SCHEDULE OF ASSESSMENTS – INDUCTION PERIOD

	Study Visit							Early Termination	NOTES
	Study Week	0	1	2	6	10	12		
	Study Day	1	8	15	43	71	85		
Visit window (days)	0	±1	±3	±3	±3	±3			
Procedure									
Eligibility Confirmation	X								
Randomization	X								Via IRT system
Complete Physical Examination						X	X		
Targeted Physical Examination	X		X	X	X				
Vital Signs	X	X	X	X	X	X	X		Heart rate, temperature, blood pressure; Take pre-dose (no more than 30 minutes pre-infusion), end of infusion, and end of observation period.
Weight	X	X	X	X	X	X	X		Needed for CDAI assessment
ECG	X					X	X		
Adverse Events Assessment	X	X	X	X	X	X	X		
Concomitant Medication	X	X	X	X	X	X	X		
Efficacy Assessments									
Ileocolonoscopy with Biopsy						X	X		Ileocolonoscopy to be performed within 10 days after Week 12 visit, or at early termination visit
Review eDiary Data from Subjects	X	X	X	X	X	X	X		Remind subjects to record in their eDiary daily
CDAI Assessment	X	X	X	X	X	X	X		
PDAI	X					X	X		
Fistula Drainage Assessment	X		X	X	X	X	X		
IBDQ	X			X		X	X		
Laboratory Testing									
CBC	X	X	X	X	X	X	X		
Chemistry Panel	X		X	X		X	X		
Fasting Lipid Panel	X					X	X		
Urinalysis	X		X	X		X	X		

	Study Visit							Early Termination	NOTES
	Study Week	0	1	2	6	10	12		
	Study Day	1	8	15	43	71	85		
Visit window (days)	0	±1	±3	±3	±3	±3			
Procedure									
Urine Pregnancy Test (WOCBP only)	X			X		X	X		
Pharmacokinetics	X ^a	X	X ^b	X ^b	X ^a	X	X		a. The PK sample at Week 0/Day 1 and Week 10 must be taken pre-dose, immediately following the end of infusion (within 30 minutes), and 1 hour after the end of infusion. b. The PK sample taken at Weeks 2 and 6 must be taken pre-dose (within 30 minutes prior to dosing).
Immunogenicity	X ^a		X ^a	X ^a		X	X		^a To be taken pre-infusion
Biomarkers									
Biomarkers	X		X	X	X	X	X		Serum at all visits; additional whole blood at Weeks 0, 6 and 12
Soluble TL1A	X		X	X	X	X	X		
hsCRP	X	X	X	X	X	X	X		
Fecal Calprotectin	X			X		X	X		
Infusion	X		X	X	X				Include date, start and stop time, volume infused, and length of the IV infusion. Infusion observation period at Week 0/Day 1 and Week 2 will be 1 hour (2 hours for subjects in Czech Republic); 30 minutes for all subsequent infusions thereafter.

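### SAP Table 2 has no hsCRP analysis window after Day 28 and gives fecal calprotectin windows at Weeks 2 and 10, where none is collected; only unscheduled replacement values are affected

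*SAP*

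**What the plan says.** SAP Section 4.4 takes data from nominal visits first. Only when the assessment is missing at a nominal visit does the window table come in: "data collected from unscheduled visits will be slotted according to the Visit Windows of Table 2 for analysis". If several unscheduled results fall in one window, the one nearest the target day is used.

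In Table 2, hsCRP appears in the Week 1 row (Days 2-11) and the first Week 2 row (Days 12-28), both listed as "Vital Signs, CBC, hsCRP, CDAI". It appears nowhere later. Fecal calprotectin is in the second Week 2 row (Days 2-28), "Fistula, Chemistry panel, Urinalysis, total sTL1A, Fecal Calprotectin". It is also in the Week 6 row (Days 29-57), the Week 10 row (Days 58-78) and the main Week 12/ET row (Days 79-92). The last two have the same list: "Vital Signs, CBC, Fistula, total sTL1A, Fecal Calprotectin, CDAI".

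The schedule differs. In SAP Appendix G the hsCRP line is marked at all six induction visits and at early termination: "hsCRP X X X X X X X". Fecal calprotectin is marked only at Weeks 0, 6, 12 and early termination. Protocol Table 2 agrees with Appendix G on both.

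SAP Table 3 (Section 6.3.1) defines hsCRP normalization at Week 12 as "hsCRP < ULN, among subjects whose baseline hsCRP" at or above ULN. Under Section 6.8.1, subjects who "fail to have an adequate efficacy assessment at that timepoint will be considered a non-responder".

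**The concern.** The window table is the only general fallback that the SAP offers when a scheduled result is missing. For hsCRP it stops at Day 28, although three more scheduled samples follow, including the one that defines a secondary endpoint. Suppose the Week 12 sample is lost and hsCRP is redrawn a few days later at an unscheduled visit. Followed literally, the table has nowhere to put that result, and non-responder imputation then records a failure although a measurement exists. The alternative is that the programmer chooses a window. In an open-label study that choice should not be left until Week 12 data can be seen.

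Calprotectin has the opposite defect. A Week 2 or Week 10 window for a marker not sampled at those visits can be filled only by unscheduled samples. Any by-visit summary there would rest on a few subjects tested for unplanned reasons.

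At stake are hsCRP normalization and the biomarker-and-clinical composite (both secondary), and the exploratory summaries of hsCRP and calprotectin over time.

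**Working it through.** No stated figure in the plan needs reproducing here. The check sets the windows of SAP Table 2 against the induction schedule (SAP Appendix G and Protocol Table 2), then applies the Section 4.4 rule.

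**Step 1. Schedule against windows, post-baseline induction visits.**

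| Assessment | Scheduled weeks | Weeks with a window | Mismatch |
|---|---|---|---|
| hsCRP | 1, 2, 6, 10, 12 | 1, 2 | 6, 10 and 12 have no window |
| Fecal calprotectin | 6, 12 | 2, 6, 10, 12 | 2 and 10 not collected |
| CBC, CDAI | 1, 2, 6, 10, 12 | 1, 2, 6, 10, 12 | none |
| Total sTL1A, fistula | 2, 6, 10, 12 | 2, 6, 10, 12 | none |
| Chemistry, urinalysis | 2, 6, 12 | 2, 6, 12 | none |
| IBDQ | 6, 12 | 6, 12 | none |
| PDAI, ECG, lipids | 12 | 12 | none |

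Of twelve assessments, ten match the schedule and two do not.

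**Step 2. Extent of the hsCRP gap.** Days 2-92 are 92 - 2 + 1 = 91 days. The uncovered part, Days 29-92, is 92 - 29 + 1 = 64 days.

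**Step 3. Which values are exposed.**
- The Week 12 visit is due on Day 85 ± 3, that is Days 82-88. An hsCRP taken there is nominal-visit data and is used without reference to Table 2. No such value is lost.
- If that value is missing, an unscheduled hsCRP on Days 79-92 has no row to enter. Sections 6.3.1 and 6.8.1 then make the subject a non-responder for hsCRP normalization.
- For the composite, a fall of at least 50% in either hsCRP or calprotectin is enough. A missing hsCRP therefore forces failure only when calprotectin does not meet the biomarker part.
- Subjects who discontinue before Week 12 are non-responders under Section 6.8.1 whatever the window.
- For the over-time summaries (SAP Table 5 and Section 6.5), an unscheduled hsCRP likewise cannot fill a missing Week 6 or Week 10 value.

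**Step 4. Size per subject.** If m subjects have elevated baseline hsCRP, one subject who had normalized but is counted as a failure lowers the rate by 100/m points. The documents do not give m. Assuming m = 40, 100/40 = 2.5 points; assuming m = 30, 100/30 = 3.3 points. On a wider assumption, one affected subject among 45 costs 100/45 = 2.2 points and three among 25 cost 300/25 = 12.0 points. All of these are upper limits, because a subject who had not normalized is classified correctly anyway.

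**The case against.** The strongest reply is that the rule bites rarely. It needs a subject who stayed in the study, has no nominal Week 12 hsCRP, has an unscheduled one in the right days, and had in fact normalized. The primary endpoint and clinical remission, the only other endpoint in the testing hierarchy (SAP Section 6.10), use neither marker. All of this stands and sets the severity. It does not remove the conflict between table and schedule.

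A reader might infer three stronger things that the documents do not support.

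- *That valid scheduled Week 12 biomarker results are discarded and imputed as failures.* They are not: the nominal-visit rule in Section 4.4 comes before the windows.
- *That a calprotectin on Days 58-78 is a Week 12 value lost to Week 10.* It precedes the Week 12 visit, which falls on Days 82-88. The 79-92 window is the same as for CDAI. Widening it to Days 58-92, as the table does for IBDQ, would be a preference.
- *That the Day 2-92 window for PDAI is an error.* The row, "ECG, Lipid panel, PDAI", groups three assessments whose only post-baseline induction measurement is Week 12/ET, so the wide window follows a consistent pattern, and early-termination values belong in a row with that label. A Day 2 PDAI could stand as an unscheduled fallback only if the nominal value were missing and no unscheduled PDAI lay nearer Day 85. PDAI change is exploratory and is not imputed.

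**Conclusion.** The point holds as a minor specification error. SAP Table 2 contradicts the schedule for two markers. The consequence that can change a result is confined to hsCRP: an unscheduled replacement on Days 79-92 for a missing Week 12 value cannot be used, and the subject is imputed as a failure for hsCRP normalization, and for the composite unless calprotectin meets the biomarker part. For calprotectin the fault is two windows with no planned sample behind them; its Week 12 fallback exists and is sound.

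The cost is 2.5 to 3.3 percentage points of the hsCRP normalization rate per affected subject who had truly normalized. This rests on an assumed 30 to 40 subjects with elevated baseline hsCRP. The documents do not say how many subjects would be affected; the conditions needed make a small number likely. The formally tested endpoints do not change.

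**What to change.** In SAP Table 2:

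- add hsCRP to the Week 6 (29-57), Week 10 (58-78) and main Week 12/ET (79-92) rows;
- remove fecal calprotectin from the Week 2 and Week 10 rows, keeping its Week 6 window at 29-57 and its Week 12/ET window at 79-92.

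No change to the PDAI window is needed.

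The fix has two limits. Unscheduled calprotectin results on Days 2-28 or 58-78 would then belong to no analysis visit, which is consistent with the schedule. And the ileocolonoscopy may fall up to 10 days after a Week 12 visit on Days 82-88, so as late as Day 98. An hsCRP redrawn at the scope on Days 93-98 would still fall outside the window, as a CDAI would.

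The cost is a few table cells, amended before database lock. No new data are needed, and no value from a nominal Week 12 visit changes.

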5 SUBJECT CHARACTERISTICS

5.1 SUBJECT DISPOSITION

Tabular summaries of subject disposition will be provided for screening and IP. These summaries will include the number of subjects screened, the number of subjects screened but not enrolled (for screening period only), and the number of subjects enrolled and treated as well as the number of subjects who discontinued the respective study period, and reasons for discontinuation.

The following subject disposition summaries will be provided based on the total number of subjects screened:

- Number of subjects screened (n)
- Number of subjects screening failures (n)
- Number of subjects enrolled (n)
- Number of subjects enrolled and treated (n)

The following subject disposition summaries will be provided based on Safety Analysis Set:

- Number of subjects completed IP (n)
- Number of subjects in FAS
- Number of subjects in PP Analysis Set
- Number of subjects discontinued prematurely during IP (n)
 - Reasons for discontinuation

	STATISTICAL ANALYSIS PLAN	
---	--------------------------------------	---

Version: 02

Status: Final

The number of subjects in Safety Analysis Set will be summarized by geographic region. A listing of subject discontinuation will be provided with a reason of discontinuation indicating period (i.e., Screening or IP).

Geographic region will be defined as follows, based on the locations of sites anticipated to participate in these studies:

- North America: Canada, United States
- Western Europe: Belgium, France, ,
- Eastern Europe: Poland, Czech, Russia, Georgia, Ukraine
- Rest of World: Australia

5.2 DEMOGRAPHICS AND BASELINE DISEASE CHARACTERISTICS

The subject's year of birth, gender, weight, height, companion diagnostic (CDx) status, prior biologic experienced, concomitant corticosteroid and immunosuppressant use, and other demographic and disease characteristics are collected at the screening visit. Age and body mass index will be calculated.

Only the year of birth is collected at screening. For the purpose of age calculation, the month and day of birth will be imputed as July 01, of the year of birth. Age is the computed as follows:

$$\text{AGE} = (\text{Informed Consent Date} - \text{Date of Birth}) / 365.25$$

Demographic and baseline characteristics (e.g., age (years), gender(male, female), race/ ethnicity, geographic region) will be summarized. The summary of demographic data and baseline disease characteristics will be provided for the Safety Analysis Set and OLE analysis set.

Baseline disease characteristics include duration of disease, CD complication, concomitant CD medication use (Steroids, immunomodulators, and aminosaliclates), and data for prior biologic use.

